6.6. Subject Early Discontinuation Criteria

Subjects MUST discontinue investigational product (and non-investigational product at the discretion of the Investigator) for any of the following reasons:

- Withdrawal of informed consent (subject's decision to withdraw for any reason)
- Any clinical adverse event (AE), laboratory abnormality or intercurrent illness which, in the opinion of the Investigator or sponsor, indicates that continued participation in the study is not in the best interest of the subject
- Pregnancy
- Termination of the study by Pfizer.
- Loss of ability to freely provide consent through imprisonment or involuntary incarceration for treatment of either a psychiatric or physical (e.g., infectious disease) illness
- Poor compliance with study procedures and visits
 - Subjects in the DBT Phase will be monitored closely for compliance with the eDiary and may not be considered for the OLE Phase, based on PI and/or Sponsor discretion if compliance is low. Subjects who demonstrate poor compliance will be discussed with the Sponsor and corrective training will be completed by the site with the subject.

- Subjects in the OLE Phase will be monitored closely for compliance with the eDiary.
- Please see [Section 6.3.5](#) for guidance on subject discontinuation based on results from the C-SSRS.
- All subjects who discontinue the DBT Phase must comply with protocol specified DBT EOT procedures as outlined in [Table 1](#). The only exception to this requirement is when a subject withdraws consent for all study procedures or loses the ability to consent freely (e.g., is imprisoned or involuntarily incarcerated for the treatment of either a psychiatric or physical illness).
- All subjects who discontinue the OLE Phase are to comply with protocol-specified OLE Week 12/EOT Visit procedures as outlined in [Table 2](#). The only exception to this requirement is when a subject withdraws consent for all study procedures or loses the ability to consent freely (e.g., is imprisoned or involuntarily incarcerated for the treatment of either a psychiatric or physical illness).
- If a participant withdraws from the study, they may request destruction of any remaining samples taken and not tested, and the investigator must document any such requests in the site study records and notify the sponsor accordingly.
- If the participant withdraws from the study and also withdraws consent for collection of future information, no further evaluations will be performed and no additional data will be collected, except for publicly available information. The sponsor may retain and continue to use any data collected before such withdrawal of consent.

6.6.1. Lost to Follow-up

A subject will be considered lost to follow-up if he or she repeatedly fails to return for scheduled visits and is unable to be contacted by the study site.

The following actions must be taken if a subject fails to return to the clinic for a required study visit:

- The site must attempt to contact the subject and reschedule the missed visit as soon as possible and counsel the subject on the importance of maintaining the assigned visit schedule and ascertain whether or not the subject wishes to and/or should continue in the study.
- Before a subject is deemed lost to follow up, the Investigator or designee must make every effort to regain contact with the subject (where possible, 3 telephone calls and, if necessary, a certified letter to the subject's last known mailing address or local equivalent methods). These contact attempts must be documented in the subject's medical record.

- Should the subject continue to be unreachable, he/she will be considered to have withdrawn from the study.

6.7. Study Early Discontinuation Criteria

The current clinical trial will be completed when the last subject finishes their final pre-specified study assessment or is otherwise permanently discontinued from the trial.

Early discontinuation of the study (in its entirety) may occur at the discretion of the Sponsor in the event there is an unacceptable shift in the benefit-risk assessment of the investigational therapy (rimegepant) for the target population under investigation (adults living with migraine who are unsuitable for triptan use). The change in benefit-risk profile of the study drug may be derived from events (adverse events, serious adverse events, etc.) occurring within the BHVS3000-406 (C4951004) study and/or any other rimegepant safety data source, including other clinical trials, toxicological studies, or spontaneous reporting of real-world evidence.

Both Pfizer and the Principal Investigator at a specific study site reserve the right to terminate the study at a given study site at any time (see [Section 14](#)).

7. STUDY DRUG MANAGEMENT

7.1. Description of Study Drug

7.1.1. Investigational Product

An investigational product, also known as investigational medicinal product in some regions, is defined as follows:

- A pharmaceutical form of an active substance or placebo being tested or used as a reference in a clinical study, including products already with a marketing authorization but used or assembled (formulated or packaged) in a way different from the authorized form, or used for an unauthorized indication, or when used to gain further information about the authorized form.
- The investigational product must be stored in a secure area according to local regulations. It is the responsibility of the Investigator to ensure that investigational product is only dispensed to study subjects. The investigational product must be dispensed only from official study sites by authorized personnel according to local regulations.
- During the DBT Phase, investigational product (study drug/ study medication) is blinded rimegepant (BHVS-3000) (PF-07899801) 75 mg ODT or matching placebo as directed.
- During the OLE Phase, investigational product (study drug/ study medication) is open-label rimegepant (BHVS-3000) (PF-07899801) 75 mg ODT as directed.

Intervention Name	Rimegepant	Placebo
Type	drug	drug
Use	Experimental	Placebo
IMP or NIMP/AxMP	IMP	IMP
Dose Formulation	Oral disintegrating tablet	Oral disintegrating tablet
Unit Dose Strength(s)	75 mg	placebo for 75-mg tablet
Dosage Level(s)	DBT phase: 75 mg (single dose) OLE phase: 75 mg per day, maximum 18 tablets per month	DBT phase : 0 mg (single dose) OLE phase: not applicable
Route of Administration	Oral	Oral
Sourcing	Provided by the sponsor	Provided by the sponsor
Packaging and Labeling	Study intervention will be provided in multi-laminated blisters, sealed with a foil backing into wallet cards. Each blister wallet will be labeled as required per country requirement.	Study intervention will be provided in multi-laminated blisters, sealed with a foil backing into wallet cards. Each blister wallet will be labeled as required per country requirement.
SRSD	IB	Not applicable

7.1.2. Concomitant Therapy

In this protocol, concomitant therapy(ies) is/are standard of care for acute treatment and acute migraine medication for migraine treatment. The standard of care and acute migraine medications are not being provided by the Sponsor.

7.1.3. Formulation

Rimegepant (BHVS-3000) (PF-07899801) is formulated as 75mg oral disintegrating tablets for which there is a matching placebo.

7.1.4. Packaging, Shipment and Storage

The product storage manager must ensure that the study drug is stored in accordance with the environmental conditions (temperature and light) as determined by the sponsor. Please see the Investigational Product Manual/Investigator Brochure for specific conditions and packaging designs. If concerns regarding the quality or appearance of the study drug arise, do not dispense the study drug and contact the sponsor/CRO immediately.

For the DBT Phase, subjects will receive 1 tablet (ODT) of blinded rimegepant 75mg or matching placebo within a blister card, heat-sealed into a wallet.

For the OLE Phase, subjects will receive blister cards containing 8 tablets (75mg ODT) of open-label Rimegepant, heat-sealed into a wallet. Subjects will receive enough IP at each dispensation visit to ensure appropriate supply between visits.

7.1.5. Dose and Administration

7.1.5.1. Double-blind Treatment Phase

In the DBT Phase, subjects will be instructed to take 1 tablet (75 mg ODT) of blinded rimegepant or matching placebo when they have a migraine attack of moderate or severe headache pain intensity that they have not already treated with acute migraine medication (see [Section 16.3 Appendix 3](#)).

7.1.5.2. Open-label Extension Phase

In the OLE Phase, subjects will receive study drug in a blister card that is heat-sealed into a wallet. Subjects will be permitted to take up to 1 tablet of open-label study drug (75 mg ODT rimegepant) per calendar day as needed for acute treatment of migraine for a maximum of 18 doses per month (month is 28 days).

- ***During the OLE Phase***

- Subjects should use open-label study drug as the first treatment of moderate or severe headache pain intensity that they have not already treated with acute migraine medication (see [Section 16.3 Appendix 3](#)).
- Throughout the 12-week OLE Phase, subjects are not permitted to use open-label study drug for the treatment of a migraine of mild or no headache pain intensity or as a rescue medication. If subjects treat a migraine of mild intensity during the OLE Phase, they are to only use permitted non-study acute migraine medication. This dosing must be recorded on the Concomitant Medication paper diary.

7.1.6. Method of Assigning Subject Identification

The Investigator or designee will need to access the Randomization and Trial Supply Management (RTSM system) in order to register each subject. Initially, after informed consent is obtained at the Screening Visit, the Investigator or designee will enter the subject into the study and obtain a subject number assignment.

At the Baseline Visit, eligible subjects will be randomized in a 1:1 ratio to rimegepant or placebo. Randomization will be stratified by history of clinically relevant CV disease (yes or no). In addition, randomization of subjects in the CV subgroup (“yes” category) will be capped at 15%. Subjects are to be categorized as “yes” if they meet the criteria for being in the CV subgroup (see [Section 16.4, Appendix 4](#), Contraindication: Cardiovascular Events, Conditions, and Procedures). Otherwise, subjects are to be categorized as “no”.

Once a subject completes the study, or if a subject is discontinued early from the study, the Investigator or designee must access the RTSM to document discontinuation of the subject from participation in the study.

7.1.7. Selection and Timing of Dose and Administration

Study drug will be assigned via the RTSM system; the system will assign specific kit numbers for all blinded study drug to be dispensed to the subject. Once a kit has been assigned it cannot be dispensed to another study subject. Sites will be responsible for recording the kit numbers dispensed to the subject on the Drug Accountability Form provided in the Regulatory Binder, as well as ensure appropriate documentation of dispensation in the subject's medical record.

For the DBT Phase, rimegepant 75 mg ODT or placebo will be assigned to subjects at the Baseline (Randomization) Visit via the RTSM system. Subjects will be instructed to administer 1 ODT when they have a migraine that is moderate or severe in headache pain intensity.

For the OLE Phase, rimegepant 75 mg ODT will be dispensed at study dispensation visits. Subjects must completely finish study drug wallets before starting new wallets.

There are no dose adjustments in this study.

Subjects **must** be instructed that they CANNOT take more than 1 tablet of study drug daily during the study and no more than 18 tablets of rimegepant per month (28 days).

7.1.8. Dose Modifications

There will be no dose adjustments in this study.

7.2. Blinding and Unblinding

Blinding is critical to the integrity of this clinical study. However, in the event of a medical emergency or pregnancy in an individual subject, in which knowledge of the investigational product is critical to the subject's management, the blind for that subject may be broken by the treating physician.

The BHV3000-406 (C4951004) study is a double-blind placebo-controlled trial being conducted in accordance with Good Clinical Practice (GCP), International Conference on Harmonisation guidelines, Ethics Committee (EC) requirements, and all applicable regulations. Within the BHV3000-406 (C4951004) study, randomization and blinding are utilized to minimize the influence of bias on the conduct of the trial and its associated outcomes.

At the Baseline Visit, eligible subjects will be randomized 1:1 across two blinded treatment arms (blinded rimegepant 75 mg or matching placebo) for the duration of the Double-Blind

Treatment (DBT) Phase. Blinded study drug assignment will be issued by centralized Interactive Response Technology (IRT) to follow block randomization of an undisclosed length. Randomization will be stratified by history of clinically relevant cardiovascular (CV) disease (yes or no; see [Section 7.1.6](#) and [16.4, Appendix 4](#)).

BHV3000-406 (C4951004) is a double-blind study in which neither the subject nor the Site staff involved in the conduct of the study or clinical evaluation of subjects are aware of study drug assignment. Sponsor staff too will be blinded to subjects' treatment assignment, except for those sponsor staff involved in the assignment or distribution of blinded study drug.

Blinded treatments (double-blind rimegepant or matching placebo) are packaged and labeled in accordance with the kit list, and supplies are dispensed through the IRT per the randomization schedule. Blinded rimegepant and blinded placebo are both oral disintegrating tablets matched in appearance, texture, and taste, and are supplied to the trial center in a manner that ensures no one involved in the conduct of the trial is aware of the specific treatment allocated to any particular subject.

Unblinding (breaking the blind for a single subject) should be considered only when knowledge of the treatment assignment is deemed by the Investigator, as essential for the proper care of the subject. The IRT will be programmed with blind-breaking instructions. In case of an emergency, the Investigator has the sole responsibility for determining if unblinding of a subject's treatment assignment is warranted. Subject safety must always be the first consideration in making such a determination. If the Investigator decides that unblinding is warranted, the Investigator should make every effort to contact the study Medical Monitor prior to unblinding a subject's treatment assignment unless this could delay further management of the subject. If a subject's treatment assignment is unblinded, the Sponsor must be notified within 24 hours after breaking the blind. The date and reason that the blind was broken must be recorded in the source documentation and CRF.

In cases of accidental unblinding, the Site should contact the Medical Monitor and ensure every attempt is made to preserve the blind for remaining site personnel.

Sponsor staff will be unblinded after the last subject completes the Double-blind Treatment End of Treatment Visit, as described in [Section 9.4](#) Once the study is complete (i.e., after the last subject completes the Follow-up Week 2 Visit) or has otherwise permanently discontinued from the trial, individual subject assignments will be made available to associated Investigators, upon request.

In the event of a Quality Assurance audit, the auditor(s) will be allowed access to unblinded study intervention records at the site(s) to verify that randomization/dispensing has been done accurately.

7.3. Treatment Compliance

Responsible study personnel will dispense the study drug. Accountability and compliance verification must be documented in the subject's study records.

DBT Phase:

Subjects have to be counseled on the importance of taking the study drug as directed for a migraine attack of moderate or severe headache pain intensity, and not taking acute migraine medication before taking study drug (see [Section 16.3](#), [Appendix 3](#)). A qualifying migraine attack is defined in [Section 4.1](#). If the subject does not have a qualifying migraine attack within 45-days of the Baseline Visit, they are to return to the clinic for their DBT EOT Visit and return their study drug. If a subject does not have a qualifying migraine attack in the DBT Phase, they are not eligible for the OLE Phase. All cases of treatment non-compliance, during the DBT Phase, are to be discussed with the Sponsor, and corrective training is to be completed and documented, prior to the subjects' enrollments into the OLE Phase.

OLE Phase:

- Treatment compliance and review of study drug doses through review of returned study drug must be assessed by site staff at each study visit. Discrepancies between review of study drug and information provided by subject must be documented in the source record. Investigators are to inform subjects that involuntary termination from the study will occur in cases where non-compliance is identified.
- Investigators must monitor subjects for possible cases of abuse of study drug (subjects taking study drug for non-therapeutic purposes, e.g., for psychoactive effects such as high or euphoria). Also, Investigators are to assess study drug accountability discrepancies (e.g., missing study drug, loss of medication, or non-compliance cases in which more study drug was used, as compared to expected). Investigators are to obtain more information and explanation from subjects when there are study drug accountability discrepancies.

7.4. Destruction and Return of Study Drug

All unused and/or partially used study drug can be sent back to the determined destruction facility only after being inspected and reconciled by the responsible Study monitor or the sponsor's designee. If it is site policy to destroy study drug on site, it is the Investigator's responsibility to ensure that arrangements have been made for the disposal, procedures for proper disposal have been established according to the applicable regulations, guidelines and institutional procedures, and appropriate records of the disposal have been documented. The unused study drugs can only be destroyed after being inspected and reconciled by the responsible Study Monitor or the Sponsor's designee.

8. ADVERSE EVENTS

An Adverse Event (AE) is defined as any new untoward medical occurrence or worsening of a pre-existing medical condition in a subject or clinical investigation subject administered an investigational (medicinal) product and that does not necessarily have a causal relationship with the study treatment. An AE can therefore be any unfavorable and unintended sign (including an abnormal laboratory finding for example) symptom, or disease temporally

associated with the use of the investigational product, whether or not considered related to the investigational product.

Adverse events can be spontaneously reported or elicited during an open-ended questioning, examination, or evaluation of a subject. In order to prevent reporting bias, subjects should not be questioned regarding the specific occurrence of one or more AEs. Non-serious Adverse events and Serious Adverse events whether related or not related to study drug, must be collected after written informed consent to participate in the study.

If a specific diagnosis or syndrome is identified by the Investigator, this must be recorded as the AE, rather than recording (as separate AEs) the individual signs/symptoms or clinically significant laboratory abnormalities known to be associated with and considered by the Investigator to be a component of, the disease/syndrome.

Definition of terms related to all Adverse Events (serious and non-serious):

Mild: Is usually transient and may require only minimal treatment or therapeutic intervention. The event does not generally interfere with usual activities of daily living.

Moderate: Is usually alleviated with additional specific therapeutic intervention. The event interferes with usual activities of daily living, causing discomfort but poses no significant or permanent risk of harm to the subject.

Severe: Interrupts usual activities of daily living, significantly affects clinical status, or may require intensive therapeutic intervention.

Life threatening: An AE is life threatening if the subject was at immediate risk of death from the event as it occurred; i.e., it does not include a reaction that if it had occurred in a more serious form might have caused death. For example, drug induced hepatitis that resolved without evidence of hepatic failure would not be considered life threatening even though drug induced hepatitis can be fatal.

Hospitalization: AEs requiring hospitalization should be considered SAEs, in accordance with the protocol. Hospitalization for elective surgery or routine clinical procedures that are not the result of AE (e.g., elective surgery for a pre-existing condition that has not worsened) need not be considered AEs or SAEs. If anything untoward is reported during the procedure, that occurrence must be reported as an AE, either 'serious' or 'non-serious' according to the usual criteria.

Assessment for Determining Relationship of AE to Study Drug:

The relatedness of each AE to study drug must be classified based on medical judgement and according to the following categories. The definitions are as follows:

Related: This category applies to AEs that are considered, with a high degree of certainty, to be related to the study drug. An AE may be considered related when it follows a temporal

090177e1a18b1bdfApproved\Approved On: 05-Sep-2024 14:18 (GMT)

sequence from the administration of study drug, it cannot reasonably be explained by the known characteristics of the subject's clinical state, environment, or toxic factors, or other modes of therapy administered to the subject. An AE may be considered related when it follows a known pattern of response to the study drug, or if the AE reappears upon re-challenge.

Possibly related (non-serious AEs only): This category applies to AEs that are considered to have a possible connection to study drug and relationship cannot be ruled out with certainty.

Unlikely related (non-serious AEs only): This category applies to AEs that do not follow a reasonable temporal sequence from the administration of the study drug. The AE may readily have been produced by the subject's clinical state, environmental or toxic factors, or other modes of therapy administered to the subject.

Unrelated: This category applies to AEs that are considered with a high degree of certainty to be due only to extraneous causes (e.g., subject's clinical state, environment, toxic factors, disease under study, etc.) and does not meet the criteria of other categories above.

There are two types of adverse events, Serious Adverse Events (SAE) and Non-Serious Adverse Events (AEs).

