Any serious adverse event must be reported immediately or no later than 24 hours after awareness of the event to Pfizer DSU either via the Pfizer SAE Submission Assistant (PSSA) tool or as a written description using the Pfizer CT SAE report form, that must be sent by facsimile (fax) to your country's Pfizer DSU. The CT SAE Report Form should only be used as a backup in the event PSSA is not operational.

If only limited information is initially available, follow-up reports are required. If an ongoing SAE changes in its intensity or relationship to study drug or if new information becomes available, a follow-up SAE report must be sent within 24 hours of the Investigator becoming aware of the updated information using the same procedure used for the transmission of the initial SAE and the same event term is to be used.

The minimum information required for an initial SAE report is:

- Sender of report (Site number, Investigator name)
- Subject identification (subject number)
- Protocol number
- SAE term (if an SAE is being reported)

The Sponsor or specified designee/authorized representative will report suspected unexpected serious adverse reactions (SUSARs) in an expedited manner (without delay) to the Regulatory Authorities and Ethics Committees concerned, in accordance with Food and Drug Administration Code of Federal Regulations (CFR) 21 CFR Parts 312 and 320, Clinical Trials Regulation EU No 536/2014 and the Detailed Guidance on collection, verification and presentation of adverse reaction reports arising from clinical trials on IPs for human use (ENTR/CT3) and also in accordance with country-specific requirements.

The Sponsor or specified designee/authorized representative shall notify the Investigator of the following information:

- Any AE that is both serious and unexpected and is suspected of being related to the use of the IP in this study or in other studies (i.e., SUSAR).
- Where required by local legislation, the Investigator shall notify his/her IRB/EC promptly of these new serious and unexpected AE(s) or significant risks to subjects.

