- If EDP occurs in a subject/subject's partner, the investigator must report this information to Pfizer Safety using the CT SAE Report Form and EDP supplemental form or via PSSA, regardless of whether an SAE has occurred. Details of the pregnancy will be collected after the start of study intervention and until 66 hours after the last dose.
- If EDP occurs in the setting of environmental exposure, the investigator must report information to Pfizer Safety using the CT SAE Report Form and EDP supplemental form or via PSSA. Since the exposure information does not pertain to the subject enrolled in the study, the information is not recorded on a CRF; however, a copy of the completed report is maintained in the investigator site file.

Follow up is conducted to obtain general information on the pregnancy and its outcome for all EDP reports with an unknown outcome. The investigator will follow the pregnancy until completion (or until pregnancy termination) and notify Pfizer Safety of the outcome as a follow up to the initial report. In the case of a live birth, the structural integrity of the neonate can be assessed at the time of birth. In the event of a termination, the reason(s) for termination should be specified and, if clinically possible, the structural integrity of the terminated fetus should be assessed by gross visual inspection (unless pre-procedure test findings are conclusive for a congenital anomaly and the findings are reported).

Abnormal pregnancy outcomes are considered SAEs. If the outcome of the pregnancy meets the criteria for an SAE (ie, ectopic pregnancy, spontaneous abortion, intrauterine fetal demise, neonatal death, or congenital anomaly [in a live born baby, a terminated fetus, an intrauterine fetal demise, or a neonatal death]), the investigator should follow the procedures for reporting SAEs. Additional information about pregnancy outcomes that are reported to Pfizer Safety as SAEs follows:

- Spontaneous abortion including miscarriage and missed abortion should be reported as an SAE;
- Neonatal deaths that occur within 1 month of birth should be reported, without regard to causality, as SAEs. In addition, infant deaths after 1 month should be reported as SAEs when the investigator assesses the infant death as related or possibly related to exposure to the study intervention.

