6.4.1.2 AE Overviews

An AE overview frequency table displays the following categories without SOC and PT: any AE; AE related to study drug; AE leading to study drug discontinuation; SAE; SAE related to study drug; medication-overuse headache AE; hepatic-related AE; hepatic-related AE leading to study drug discontinuation; potential drug abuse AE; cardiovascular AE; suicidality AE; hypertension AE; and Raynaud’s phenomenon AE.

AE overview frequency tables are provided for the following safety analysis periods and analysis sets:

- On-DBT for the DBT safety analysis set
- On-DBT for the DBT safety analysis set by subgroup level and overall for all high-level safety subgroups of interest described in Section 4.3.2 for each treatment group. Results support exploratory objective #17.
- Post-DBT pre-OL rimegepant for the interim safety analysis set
- On-OL rimegepant for the OL rimegepant safety analysis set

- On-OL rimegepant for the OL rimegepant safety analysis set by subgroup level and overall for all high-level safety subgroups of interest specified in Section 4.3.2. Results support exploratory objective #17.
- Follow-up for the follow-up safety analysis set.

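### Protocol Section 8 offers no valid causality rating for a serious adverse event whose link to study drug is possible but unproven

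*Protocol*

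**What the plan says.** Protocol Section 8, in the part on assessing relationship to study drug, makes the scale compulsory: "The relatedness of each AE to study drug must be classified based on medical judgement and according to the following categories". Four categories follow.

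- Related: "This category applies to AEs that are considered, with a high degree of certainty, to be related to the study drug".
- Possibly related: "Possibly related (non-serious AEs only): This category applies to AEs that are considered to have a possible connection to study drug".
- Unlikely related: "Unlikely related (non-serious AEs only): This category applies to AEs that do not follow a reasonable temporal sequence".
- Unrelated: open to all events. It requires equally strong certainty that causes other than the drug are the whole explanation, and that the event meets none of the other definitions.

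Other sections use different causality language for serious events. Section 8.1.2 describes a SUSAR as "Any AE that is both serious and unexpected and is suspected of being related to the use of the IP". Section 8.5.1 makes a death more than one month after birth reportable as an SAE when the investigator judges the "infant death as related or possibly related to exposure to the study intervention".

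Protocol Section 9.3.2 leaves the relationship rating to investigators. SAP Section 6.4.1.2 lists the overview rows "SAE; SAE related to study drug". SAP Section 6.4.1 takes the definition of a drug-related AE from the Core SAP, which is a separate document.

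**The concern.** A two-level scale is sound if its levels cover every case. Here the levels sit at opposite ends and leave the middle empty, and the middle is where many serious events start. The scale is therefore coarser for serious events than for non-serious ones.

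The stake is the accuracy of the recorded causality of SAEs. An investigator who thinks the drug might have contributed cannot record that view. Whichever permitted rating is chosen claims a certainty the investigator does not have, and two sites with the same event and the same opinion can record opposite answers. The study has no data monitoring committee (Protocol Section 10.2), so attribution rests with the investigators and the sponsor.

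**Working it through.** No arithmetic beyond a count applies, and the plan states no figure to reproduce. The check sets the definitions against the views an investigator might hold.

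| Investigator's view | Non-serious AE | SAE |
|---|---|---|
| Strong certainty that the drug is the cause | Related | Related |
| Possible link, cannot be ruled out | Possibly related | none |
| Poor fit in time, another cause readily available, but not certain | Unlikely related | none |
| Strong certainty that only other causes apply | Unrelated | Unrelated |

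Four categories are listed and two are closed to SAEs, so 4 − 2 = 2 remain. Both need strong certainty. The number that cover an uncertain SAE is 0.

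**The protocol itself generates such events.** Section 8.4 requires potential Hy's law cases to be reported as SAEs before the results of the work-up are in, and treats them as confirmed only once alternative causes have been excluded. At first report the cause is by design unknown. Related fails because certainty is lacking, and Unrelated fails for the same reason. Section 8.2.1 gives a second route: a non-serious AE that becomes serious is then reported as an SAE. If it was rated Possibly related, it loses its category although nobody's view of causality has changed.

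**Comparison with the other sections.** Section 8.1.2 works from suspicion, a lower threshold than the certainty in Section 8. An SAE can be suspected and still fail the definition of Related. Section 8.5.1 uses a possible relationship as a trigger for a serious event, a grade that Section 8 closes to SAEs. I found no text in either document that says how to rate an SAE of uncertain relationship.

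**Where the rating goes.**

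1. Causality is among the SAE data items the investigator must enter (Section 8.1.2), and so is an input to the sponsor's SUSAR assessment.
2. After the Follow-up Week 2 Visit, the investigator is asked to report an SAE only when it is thought to be due to study drug or protocol procedures (Sections 6.3 and 8.1.2). If the strict definition of Related is carried over to this step, it could influence whether a late SAE is reported at all.
3. It feeds the related-SAE row of the AE overview (SAP Section 6.4.1.2) and the tables of related AEs on double-blind treatment and on open-label rimegepant (SAP Sections 6.4.1.3 and 6.4.1.5).

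A rule in the Core SAP can group recorded ratings, but it cannot recover a possible link that was never recorded.

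**The case against.** The strongest reply is that little depends on this rating. Much of that stands. During the study every SAE is collected whatever its rating and reaches the sponsor's safety unit within 24 hours. The sponsor makes the SUSAR report, and nothing says its judgement is bound by the site's rating. A change in the assessed relationship of an ongoing SAE must be sent as a follow-up report, so a first rating can be revised. All SAEs and all cardiovascular AEs are tabulated regardless of relatedness. The narrative listing covers all SAEs on rimegepant or during follow-up, with no causality condition (SAP Section 6.4.6). The infant-death wording concerns a reporting trigger for an offspring event, so it shows inconsistent vocabulary rather than a rival rule for rating subjects' events.

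A reader might infer more than the text supports: that uncertain SAEs will slide into Unrelated, that the related-SAE row is therefore biased downward, and that a cardiovascular SAE in the CV stratum could hardly ever be called Related. The documents do not support this. Unrelated also demands strong certainty, so an uncertain event fails it too. The sentences that elaborate Related are permissive: they say when an event may be so rated and offer more than one route, including a known response pattern or recurrence on re-challenge. The grouping rule behind the SAP row is in the Core SAP and cannot be seen. The CV stratum cap, 0.15 × 600 = 90 subjects, limits enrolment across both arms and is not a count of affected events. Uncontrolled, unstable or recently diagnosed cardiovascular disease is also excluded (Section 5.3).

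None of this supplies the missing category. The safeguards protect capture and counts, while the recorded causality of an uncertain SAE is still forced.

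**Conclusion.** The rule is wrong as written and should be fixed. It is more than missing detail: followed literally, it makes the investigator enter a causality rating that misstates their view whenever the link between an SAE and study drug is possible but unproven.

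The effect is confined to recorded SAE causality and its uses: SUSAR assessment, SAE reports after the Follow-up Week 2 Visit, and the SAP's related-event row and tables. In-study SAE capture, 24-hour reporting and total SAE counts are untouched. The number of affected events cannot be given, because no expected SAE count is stated.

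Under-attribution is the main risk, because a missed suspicion costs more than a surplus one. It remains a risk and not a predicted direction of error. The conclusion assumes that sites apply Section 8 as worded and that no case report form instruction outside these documents overrides it.

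**What to change.** Reconcile Protocol Sections 8, 8.1.2 and 8.5.1 in one of two ways:

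- remove the restriction to non-serious events from Possibly related and Unlikely related; or
- keep two levels for SAEs, define Related as a reasonable possibility of a causal link, and define Unrelated as its complement so that every SAE fits exactly one.

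In either case, state which ratings count as suspected for Section 8.1.2 and which enter the related-SAE row in SAP Section 6.4.1.2. Put the grouping in this SAP rather than only in the Core SAP.

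The cost is protocol wording and the SAE causality pick-list, with no new visits or procedures. A few more SAEs may count as related and be assessed for expedited reporting. SAEs already rated need their causality confirmed by the sites under the corrected definitions, so that two scales are not mixed in one table. For double-blind events this is best done before the treatment codes are opened at the primary completion database lock, if that has not yet happened.
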